6.1 Analysis of Primary Endpoint

6.1.1 Definition of Analysis Samples

- Target Population
The target population for the POSITIVE trial is patients who are at least 18 who have a clinical diagnosis of Acute Ischemic Stroke who are ineligible for or refractory to treatment with IV-tPA and able to begin the thrombectomy procedure within a 6-12 hour time window of symptom onset or time last seen normal and as selected by physiologic imaging criteria.
- Intent to Treat Sample
As the primary analysis, all efficacy and safety outcome measures will be analyzed under the intent-to-treat (ITT) principle. Under this principle, the evaluable sample includes all subjects who are randomized. Each subject will be analyzed according to the treatment group to which they were assigned at randomization.
- Per Protocol Sample
In addition to the defined ITT analysis sample, a per-protocol sample is defined as a subset of the ITT sample. This sample will be used for secondary sensitivity analyses of the primary and secondary outcomes. The per-protocol sample will include all randomized subjects that do not have the following protocol violations or deviations:
 - a. Eligibility violation
 - b. Treatment crossover
 - c. Missing 90 day primary outcome (not including missing due to death prior to the 90 days)

7. General Statistical Considerations

The POSITIVE Trial is a multicenter, randomized, Phase III clinical trial investigating the safety and efficacy of endovascular mechanical thrombectomy administration in acute ischemic stroke patients ineligible for or refractory to treatment with IV-tPA presenting within a 6-12 hour time window as selected by physiologic imaging criteria compared to best MT. The primary hypothesis to be tested is that treatment with endovascular mechanical thrombectomy will improve outcomes at 90 days as compared to the best MT group. Each eligible subject will be randomized in a 1:1 ratio to either the endovascular mechanical thrombectomy or the best MT treatment group with a stratified randomization by NIHSS (<20 vs. ≥20) within each center to balance randomization. This variable was chosen because of the known association with outcome. Randomization will take place centrally through the web-based REDCap database system. The centrally controlled randomization will help ensure the treatment balance at any interim analysis as well as in the final analysis.

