7.4 Secondary Statistical Analysis

7.4.1 Secondary Outcomes

- 90-day global disability in the 6-12 hr cohort assessed via the proportion of patients achieving a mRS of 0-2
- Proportion of patients with good functional recovery for the 6-12 hr cohort as defined by mRS 0-2 at 90 days

- Mortality at 30 and 90 days
- Intracranial hemorrhage with neurological deterioration (NIHSS worsening >4) within 24 hours of randomization
- Procedure related serious adverse events (SAE's)
- Arterial revascularization measured by TIC1 2b or 3 following device use

Secondary outcome endpoints will be compared between randomized groups in an ITT fashion; with overall Type I error controlled using hierarchical testing. That is, if statistical significance is observed on the primary effectiveness endpoint, the secondary clinical efficacy endpoints will then be tested in sequential fashion each at a two-sided alpha level of 0.05, with testing ceasing once a null hypothesis cannot be rejected. The statistical tests will be performed in the order specified above.

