7.5 Safety Analysis

7.5.1 Safety Outcomes

Several specific adverse events will be monitored throughout the study. However the primary safety outcomes to be assessed at completion of the trial are:

- Symptomatic intracranial hemorrhage at 24 hours post-randomization
- Asymptomatic intracranial hemorrhage at 24 hours post-randomization
- Intracranial hemorrhage within 90 days of hospital discharge
- Clinically significant complications (pneumonia, sepsis, UTI, etc.) at time of discharge or 7 days post randomization, whichever comes first.
- Mortality rates at 30 days post-hospital discharge
- Mortality rates at 90 days post-hospital discharge
- Treatment-related SAEs up to 48 hours post-randomization

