7.5.2 Interim Safety Monitoring

7.5.2.1 Stopping the Trial Based on Interim Safety Data

The DSMB will receive periodic safety reports of all AEs and SAEs. In addition, the treatment-related SAE's occurring within 48 hours of randomization will be monitored as a safety outcome along with the following:

- Symptomatic intracranial hemorrhage within 24 hours of randomization
- Asymptomatic intracranial hemorrhage within 24 hours of randomization
- Mortality rates at 30 days post-hospital discharge
- Mortality rates at 90 days post-hospital discharge
- Treatment-related SAEs during the study
- All SAE's during the study
- Major non- intracranial hemorrhage bleeding complications during hospitalization
- Recurrent stroke within 90 days of hospital discharge

Additional details of the monitoring plan will be included in the study SAP and Monitoring Plan.

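### Mortality, late ICH and recurrent stroke are counted from hospital discharge, while visits and SAE recording run from randomization, so these named safety rates miss or leave undefined in-hospital events and their 90-day windows outlast follow-up

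*Combined protocol and SAP*

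**What the plan says.** Section 7.5.1 names the primary safety outcomes to be assessed when the trial is complete. Three of them start at discharge: mortality at 30 days, "Mortality rates at 90 days post-hospital discharge" and "Intracranial hemorrhage within 90 days of hospital discharge". The other two ICH outcomes in that list, symptomatic and asymptomatic, are set at 24 hours after randomization.

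Section 7.5.2.1 lists what is monitored during the trial. It includes "Mortality rates at 30 days post-hospital discharge", the matching 90-day item and "Recurrent stroke within 90 days of hospital discharge". It closes with "Additional details of the monitoring plan will be included in the study SAP and Monitoring Plan".

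The data behind these items follow a different clock. Section 4.4 and Table 1 schedule visits at 24 hours, at 7 days or discharge, at 30 days and at 90 days, all from randomization, with a tolerance of 14 days on the last two. Sections 5.9.3, 16 and 16.2 record SAEs from randomization to the 90-day visit. No visit is scheduled 30 or 90 days after discharge.

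Section 6.1.1 says that "all efficacy and safety outcome measures will be analyzed under the intent-to-treat (ITT) principle" and that "the evaluable sample includes all subjects who are randomized". The secondary endpoint in 7.4.1 reads "Mortality at 30 and 90 days", with no time origin written.

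**The concern.** A rate needs a time origin that every randomized patient has and a window that follow-up covers. Discharge gives neither. A patient who dies in hospital is never discharged alive, so it is unclear whether that death counts. A patient who bleeds or has a second stroke on the ward does so before the clock starts. For everyone else, the 90-day window closes after the nominal end of follow-up.

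Discharge also happens after randomization, and its timing may differ between thrombectomy and medical therapy. A discharge clock then compares the arms over different stretches of the illness, which weakens the intention-to-treat safety comparison that 6.1.1 promises.

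At stake are named primary safety outcomes and rates that the DSMB is to watch. Two analysts following the text could report different mortality from the same data. The late-ICH and recurrent-stroke rates would leave out the inpatient period.

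**Working it through.** The plan states no figure that depends on these anchors, so there is nothing to reproduce. The check compares the windows with the follow-up.

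**Inputs.** Final visit on day V = 90 ± 14, so day 76 to 104 (4.4). SAE recording ends at that visit (16, 16.2). The 24-hour assessment may fall as late as 36 hours (4.4, 5.6). Length of stay L, in days from randomization, is not given; 3, 7, 14 and 28 are assumptions.

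**Formulas.**
- Time before discharge in which an ICH fits no outcome in 7.5.1: L − 1 days, or L − 1.5 if the 24-hour item extends to a scan at 36 hours.
- Time in which a recurrent stroke is outside its item in 7.5.2.1: L days.
- End of a 90-day window: day 90 + L.
- Unobserved end of that window: max(0, 90 + L − V).

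| L (assumed) | ICH not covered | Stroke not covered | Window ends | Unobserved, V = 90 | V = 76 | V = 104 |
|---|---|---|---|---|---|---|
| 3 | 2 (1.5) | 3 | day 93 | 3 | 17 | 0 |
| 7 | 6 (5.5) | 7 | day 97 | 7 | 21 | 0 |
| 14 | 13 (12.5) | 14 | day 104 | 14 | 28 | 0 |
| 28 | 27 (26.5) | 28 | day 118 | 28 | 42 | 14 |

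In the V = 76 column, 14 days of each entry come from the visit tolerance and only L days from the discharge anchor. The 30-day windows end on day 30 + L (33, 37, 44, 58), before the earliest permitted final visit, so the unobserved tail concerns only the 90-day items.

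**Arm differences.** If typical stays were 7 days in one arm and 14 in the other (assumed), the 90-day items would cover days 7–97 in one and 14–104 in the other.

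**Mortality, as an illustration only.** Let m be 90-day mortality and f the share of deaths that occur in hospital (assumed). With all randomized patients as denominator, leaving out in-hospital deaths gives m(1 − f). With patients discharged alive as denominator, it gives m(1 − f)/(1 − mf). Take m = 26%, the pilot thrombectomy series in section 1, applied to both arms by assumption:

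| f | In-hospital deaths counted | Left out, all randomized | Left out, discharged alive |
|---|---|---|---|
| 0.25 | 26% | 19.5% | 19.5/93.5 = 20.9% |
| 0.50 | 26% | 13.0% | 13.0/87.0 = 14.9% |
| 0.75 | 26% | 6.5% | 6.5/80.5 = 8.1% |

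With 26% mortality in both arms but f = 0.60 in one and 0.40 in the other, leaving out in-hospital deaths among all randomized gives 10.4% against 15.6%. Counting them gives 26% against 26%.

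**The case against.** The strongest reply is that nothing is lost. SAEs are recorded from randomization. An unblinded Safety Monitor reviews each one as it occurs and reports to the DSMB (5.9.3), and 7.5.2.1 has the DSMB monitor all SAEs during the study. Section 5.9.3 asks for a detailed report of symptomatic hemorrhage with no 24-hour or discharge limit. Deaths are scored mRS 6 (7.3) and count in secondary mortality. All of this stands. A reader might infer that in-hospital deaths and bleeds go unseen, or that a stopping rule would fail; the documents support neither. The supplied text attaches no numerical threshold to these rates.

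Second, the mortality items say at, not within, 30 or 90 days. With 6.1.1 putting every randomized patient in the safety analysis, a cumulative reading that includes in-hospital deaths is natural. This also stands: mortality is ambiguous, and the text does not say that in-hospital deaths are excluded. But the cumulative reading is unstated, leaves the tail beyond the 90-day visit in place, and does nothing for late ICH or recurrent stroke, which are worded as windows that open at discharge.

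Third, a separate SAP and Monitoring Plan may settle the matter. Section 7.5.2.1 does defer to them, and they are not in the supplied text. The deferral covers further monitoring detail, however, and 7.5.1, which defines the primary safety outcomes, carries no such deferral.

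**Conclusion.** The point holds as a fault in how a few named rates are defined. Two parts follow from the wording alone: ICH between the 24-hour assessment and discharge has no outcome in 7.5.1, and recurrent stroke before discharge is outside its item in 7.5.2.1. A third also follows: each 90-day window runs L days past a day-90 visit and, for L above 14, past even a day-104 visit. The mortality numerator is an ambiguity rather than an error.

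The size depends on length of stay and on the in-hospital share of deaths. The documents give neither for this population, so the day counts rest on assumed stays and the mortality percentages on assumed shares and a choice of denominator; the percentages show only that the choice can matter. Section 1 cites 25% mortality while hospitalized in a national inpatient sample of thrombectomy patients. That is a different population, and it shows only that the in-hospital share cannot be presumed small. The primary efficacy analysis and the sample size are unaffected.

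**What to change.** In 7.5.1 and 7.5.2.1, count 30- and 90-day mortality from randomization. In 7.5.2.1, count 90-day recurrent stroke from randomization. State that in-hospital events are included and that the denominator is all randomized patients, as in 6.1.1.

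In 7.5.1, define late ICH as ICH after the patient's 24-hour assessment and through day 90 after randomization. This closes the gap without counting the 24-hour events twice. Report it as ICH recorded as an SAE or seen on imaging actually done, because asymptomatic hemorrhage is not an SAE (5.9.3) and Table 1 schedules no routine scan after 24 hours.

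The cost is almost entirely wording, since these windows then match the visits and SAE recording already planned. Recurrent stroke needs one confirmation: 5.9.3 does not name it, and non-serious events are recorded only to day 7 or discharge, so the rate rests on SAE recording. There are two small downsides. The mortality items will coincide with the secondary mortality endpoint if that is also read from randomization. And max(0, 90 − V), at most 14 days, stays unobserved for patients whose final visit falls on days 76–89.

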7.5.2 Interim Safety Monitoring

7.5.2.1 Stopping the Trial Based on Interim Safety Data

The DSMB will receive periodic safety reports of all AEs and SAEs. In addition, the treatment-related SAE's occurring within 48 hours of randomization will be monitored as a safety outcome along with the following:

- Symptomatic intracranial hemorrhage within 24 hours of randomization
- Asymptomatic intracranial hemorrhage within 24 hours of randomization
- Mortality rates at 30 days post-hospital discharge
- Mortality rates at 90 days post-hospital discharge
- Treatment-related SAEs during the study
- All SAE's during the study
- Major non- intracranial hemorrhage bleeding complications during hospitalization
- Recurrent stroke within 90 days of hospital discharge

Additional details of the monitoring plan will be included in the study SAP and Monitoring Plan.

7.6 Blinding

This study is not blinded. Blinding is difficult, if not impossible, from a clinical perspective. It is not possible to blind the Investigator who treats the patient, nor is it possible to blind the internal review committee (IRC) members. Additionally, physicians treating subjects who experience an adverse event after must know how the stroke was treated in order to effectively report the adverse event and plan further treatment. Blinding the study is not required for interpretation of study outcomes. However to avoid bias in study results, the person performing the primary outcome assessment at 90 days

must be blinded to the subject's treatment assignment and have not been associated with the care of the subject during the acute treatment phase.

8. Study Withdrawal

Subjects may be terminated or withdrawn from the study for the following reasons:

- Voluntary withdrawal of consent— meaning that a subject voluntarily chooses not to participate further in the study. All data collected up to the withdrawal of consent will be maintained in the study database.
- Lost to follow-up — defined as a subject who is more than one month late to a study visit and for whom 5 documented telephone attempts to contact the subject and at least one certified letter were unsuccessful.
- Subjects may also be withdrawn at the investigator's discretion if within their best interest.

8.1 Unattended Visits

Any study subject who does not attend a scheduled follow-up visit should be contacted by site personnel to determine the reason for the missed appointment(s). If the missed visit was due to a serious adverse event, (e.g., re-hospitalization) an Adverse Event report must be completed in the study database and any reporting requirements met.

9. Data Safety Monitoring Board (DSMB)

A DSMB will be comprised of 4 members not participating in the trial and will include a neuroradiologist, neurologist, neurosurgeon and statistician. The DSMB will exercise review of the overall safety of the trial, periodically review all adverse events occurring in the trial, and make recommendations to adjustments in the study protocol, should any be considered necessary for safety or other related reasons.

10. Trial Operating Committee

This study will have a trial operating committee (TOC) whose goal is to oversee trial operations. The TOC will consist of the study PI, statistical PI, project managers, data managers, and others deemed necessary in overseeing the day to day operations of the trial. The TOC will review study progress, study conduct at individual clinical sites, other clinical site performance measures, and blinded DSMB reports.

11. Scientific Advisory Committee (SAC)

This committee will be comprised of prominent investigators who are not part of this study. The SAC will function as an independent group that is charged with critically reviewing all aspects of the trial and advising the TOC on new scientific developments that may affect the design or conduct of this trial. Removed from the day-to-day operation of the trial, this committee is charged with providing a frank appraisal of the overall success of the TOC in achieving its operational objectives related to recruitment, data quality, and safety. This committee will be available to the Principal Investigators and TOC to consult on any problems that occur during the trial.

Unlike the Data Safety Monitoring Board, however, the SAC will not review data on overall rates of outcome or interim effectiveness data. The SAC does not have authority

to change the research protocol; it may recommend changes, but these would have to be approved by the Data Safety Monitoring Board before implementation.

The SAC will meet once prior to the start of enrollment to review the final protocol and procedure manual. Thereafter, it will meet as often as it deems necessary. At least one week before each meeting, the Principal Investigator will provide a progress report to the SAC to include all information requested by its Chair. It is anticipated that this report will require contributions from the respective centers in this study.

12. Steering Committee (SC)

The Steering Committee will be comprised of the trial PI's, principal investigators from the 5 top enrolling centers, statistician, and a representative from each corporate sponsor. The SC will be responsible for overall supervision and execution of the trial including adherence to protocol, progress of enrollment, patient safety, and consideration of new information. While daily trial management is the responsibility of the TOC, the TOC will provide key input to the SC for study planning, execution and data presentation.

12.1. Study Management

As the study Principal Investigator, [name] has overall responsibility for the conduct of the study according to 21 CFR 812, 21 CFR Part 50, Good Clinical Practice (GCP) Guidelines (Guidance for Industry, E6 Good Clinical Practice Consolidated Guidance, ICH, April 1996), ISO 14155: Part 1 and 2, the Declaration of Helsinki, Medical Device Directive, Annex X, FDA and all applicable regulatory requirements. For this study, [name] will have certain direct responsibilities and will delegate other duties to appropriately qualified individuals. All personnel participating in the conduct of this clinical trial will be qualified by training, education, and experience to perform his or her respective tasks.

*NOTE: A complete list of participating investigators will be maintained and will be available upon request.

13. Investigator Responsibilities

The Investigator(s) shall be responsible for the day-to-day conduct of the investigation as well as for ensuring that the investigation is conducted according to all signed agreements, applicable elements of ISO 14155, the Clinical Investigational Plan, applicable FDA regulations, and the principles that have their origin in the Declaration of Helsinki.

The investigator is also responsible for having control of the device under investigation, for protecting the rights, safety and welfare of subject's under the investigator's care and for obtaining informed consent in accordance with 21 CFR Part 50. Each Investigator must sign the Investigator Agreement (or an equivalent and a Financial Disclosure) prior to becoming eligible to enroll subjects in this trial.

Responsibilities of the Investigator include, but are not limited to:

- Ensuring that IRB approval is obtained prior to undertaking the trial at a clinical site
- Ensuring that participation of a subject in a clinical trial includes obtaining written informed consent prior to randomization and/or other non-standard of care study-related assessments
- Providing the study sponsor with accurate and complete financial information per 21 CFR Part 54
- Ensuring that all personnel assisting with the clinical trial are adequately informed and understand their trial-related duties and functions

It is recommended that each site identify a study coordinator for this study. Working with and under the authority of the clinical site Principal Investigator, the study coordinator assures that all study requirements are fulfilled and serves as the contact person at the site for all aspects of study administration.

The Investigator will allow direct access to source data/documents for trial related monitoring, auditing, IRB/EC review, and regulatory inspection. Also, the investigator will allow auditing of their clinical investigational procedure(s).

14. Required Documents from the Investigator

At a minimum, the investigational site will provide the following documents to the study sponsor:

- Signed Investigator Agreement
- Written and dated IRB/EC approval
- Written and dated IRB/EC approval for ICF document
- IRB/EC approval for any other written documents to be provided to the study subject (e.g., advertising)
- HIPAA documentation (if applicable)
- Investigator and Co-Investigators' current Curriculum Vitae*
- Current medical licenses
- Any other relevant documents requested by the study sponsor or the reviewing IRB/EC or other regulatory authorities,
- FDA Form 3454 or 3455 (or equivalent) regarding financial interests
- Fully executed contract
- Ongoing IRB approval documents
- Source Documents for data verification
- Site Delegation of Authority Log

* With regard to the Sub-Investigators current CVs, the study may begin once the CV of the site PI, IRB approval and IRB approved consent and privacy statement, the investigator's agreement, Medical License, and financial disclosures, fully-executed contract, and others listed above, have been received. No additional Investigators may participate in the study, however, until a copy of their CV and all other required documents have been provided to the study sponsor.

15. Investigator Records

The Investigator must ensure that all study subject records are stored for at least 6 years after the end of the clinical study. To avoid error, the study site should contact [name] prior to the destruction of study records to ensure that they no longer need to be retained. In addition, [name] should be contacted if the Investigator plans to leave the investigational site so that arrangements can be made for the handling or transferring of study records.

The Investigator will also maintain original source documents from which study-related data are derived, which include, but are not limited to:

- Clinic progress notes recording subject's medical history and medications
- Medical charts with operative reports and subject condition upon discharge
- Medical records regarding AE's/SAE's, including treatment and clinical outcome
- Results of diagnostic examinations, imaging (such as x-rays, MRIs), as well as the report of the radiologist's reading/interpretation of diagnostic imaging
- Signed notes of phone calls and/or correspondence indicating investigational site's attempts to follow study subjects at the required follow-up visits until subject's participation in the study is complete or terminated
- Records relating to patient death (e.g., death certificate, autopsy report, if available, or terminal medical records)

